Statistical Analysis Plan

Title: Friendship Bench Mental Health Intervention for Adolescent Girls and Young Women in South African PrEP Delivery Settings

NCT05664490

Date Created: 15 January 2024 **Last Updated:** 29 July 2024 Drafted by: [name] MPH; [name]; [name]

Statistical Team

University of California San Francisco, San Francisco, USA

University of the Witwatersrand, Johannesburg, South Africa

Table of Contents

Background and Rationale	. 3
Study Objectives and Hypothesis	. 3
Study Design	. 4
Schema	. 5
Overview of Study Design	. 7
Sample size and power calculations	. 8
Data Analysis	. 8

Background and Rationale

The purpose of this study is to adapt and test the Friendship Bench for South African adolescent girls and young women (AGYW) attending PrEP services, using a hybrid effectiveness-implementation trial.

The Friendship Bench is an ideal starting point for treating mild-to-moderate symptoms of common mental disorders among AGYW in PrEP delivery settings, given that it was designed for and tested in a similar African context. The proposed study will test and optimize the Friendship Bench for AGYW with mental health needs in South African/PrEP programs ("Youth Friendship Bench SA").

Study Objectives and Hypotheses

The co-primary objectives of this study are:

- To compare the proportion of young South African women who adhere well to PrEP (based on tenofovir [TFV] levels from a urine point-of-care [POC] assay) between those receiving the Youth Friendship Bench SA plus standard-of-care (SOC) mental health services versus receipt of standard-of-care services alone, after 3 months
- To compare the proportion of young South African women with reduced symptoms of common mental disorders (based on SRQ-20 score) between those receiving the Youth Friendship Bench SA plus standard-of-care mental health services versus receiving standard-of-care services alone, after 3 months

The secondary objectives of this study are:

- To compare the proportion of young South African women who adhere well to PrEP (based on tenofovir [TFV] levels from a urine point-of-care [POC] assay) between those Youth Friendship Bench SA, Version 1.030August 202222receiving the Youth Friendship Bench SA plus standard-of-care mental health services versus receipt of standard-of-care services alone, after 4 weeks.
- To assess the correlates of PrEP adherence, after adjusting for study arm, including sociodemographic factors and psychosocial and behavioral characteristics.

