Predictor(s) of interest: Randomized intervention arm, either the Youth Friendship Bench SA plus SOC or SOC services alone groups.

Statistical analyses:

- 1) We will compute descriptive statistics to describe the full study population of randomized individuals at baseline and to describe retention over time in both arms of the intervention. We will also summarize reasons for discontinuing PrEP.
- 2) We will compute descriptive statistics for missing data, including the pattern of missingness across visits for both arms of the intervention, and factors associated with missingness. All information from participants with missing data will be examined to determine if any pattern is evident that would account for the missingness.
- 3) Primary analysis: We will conduct an intent-to-treat analysis using a Poisson regression with robust standard errors to assess the effect of the Youth Friendship Bench SA plus SOC intervention compared to SOC services alone on TFV levels measured in urine (with PrEP adherence defined as TFV ≥1500 ng/mL) at 4 weeks after randomization. The main effect can be interpreted as the difference in PrEP adherence at 4 weeks between the SA plus SOC arm and SOC only arm of the intervention. The effect of the intervention will be estimated as a relative risk (RR) from the Poisson regression model, with treatment arm assigned at first randomization as the only predictor.

Secondary Analysis 2: To assess the correlates of PrEP adherence, after adjusting for study arm, including sociodemographic factors and psychosocial and behavioral characteristics.

Analysis population: South African AGYW participants enrolled and randomized in a 1:1 ratio to either the Youth Friendship Bench SA plus SOC intervention or the SOC services alone arm.

Outcome: correlates of PrEP adherence at 12 weeks, adjusted for study arm

Predictor(s) of interest: Randomized intervention arm, either the Youth Friendship Bench SA plus SOC or SOC services alone groups; and covariates described below.

- Covariate characteristics assessed at baseline and follow-up may include Sociodemographic characteristics; sexual behaviors; gender-based violence (GBV); symptoms of common mental disorders; self-esteem; and level of engagement with the intervention.
- Other covariates will be selected via the processes described below.

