Covariate selection process for multivariable models: We will use a combination of consulting previous research, univariate analyses, and forward stepwise selection to determine which sociodemographic factors and psychosocial and behavioral characteristics will be included in our multivariable models:

 We will first determine which variables to include based on pre-existing research and theories. We will consult pre-existing research on variables associated with PrEP adherence to narrow down our list of variables to include in our secondary analysis. We will also create a rough theoretical "model" of the relationship between associated variables and our outcome of PrEP adherence to ensure there are no temporality concerns and to help us understand which variables may be mediators/moderators of others.

- 2) Before building our model, we will conduct univariate chi-squared tests to assess the relationship between each covariate selected from the previously defined step and PrEP adherence. Based on this test, variables with a p-value greater than alpha-level of 0.05 will be included in our multivariable model.
- 3) After selecting our covariates, we will build our model using forward stepwise selection. Broadly, forward selection begins with a null model and adds one independent variable at a time, starting with the variable whose inclusion gives the most statistically significant improvement of the fit by looking at the Akaike Information Criterion (AIC) and Bayesian Information Criterion (BIC) model fit statistics. AIC penalizes the number of parameters to avoid overfitting. In a Poisson model, a lower AIC indicates a better model fit. BIC is similar to AIC but has greater penalties for more complex models. Similarly, a lower BIC indicates a better model fit. We will repeat this process until no additions significantly improve the model fit. The final model's AIC and BIC will be presented in the table.

Statistical analyses:

- We will conduct an intent-to-treat analysis using a Poisson regression with robust standard errors to assess the association of selected covariates on TFV levels measured in urine (with PrEP adherence defined as TFV ³1500 ng/mL) at 12 weeks, adjusting for study arm. The effect of each covariate on PrEP adherence will be estimated as a relative risk (RR) from the Poisson regression model.

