- 2) We will also conduct a per-protocol analysis using the same procedures described above, but only amongst participants who received full doses of the Youth Friendship Bench SA plus SOC intervention or SOC only.

Secondary Analysis 3: To assess the correlates of symptoms of common mental disorders, after adjusting for study arm, including sociodemographic factors and psychosocial and behavioral characteristics.

Analysis population: South African AGYW participants enrolled and randomized in a 1:1 ratio to either the Youth Friendship Bench SA plus SOC intervention or the SOC services alone arm.

Outcome: correlates of common mental disorder symptoms at 12 weeks, adjusted for study arm [categorical SRQ variable; categories: >7, <7]

Predictor(s) of interest: Randomized intervention arm, either the Youth Friendship Bench SA plus SOC or SOC services alone groups; and covariates described below.

• Covariate characteristics assessed at baseline and follow-up may include Sociodemographic characteristics; sexual behaviors; gender-based violence (GBV); self-esteem; and level of engagement with the intervention

Covariate selection process for multivariable models: We will use the same process described above using separate theoretical guidelines and univariable analyses for variable selection.

Statistical analyses:

1) We will conduct an intent-to-treat analysis using a Poisson regression with robust standard errors to assess the association of selected covariates on reduced symptoms of common mental disorders at 12 weeks, adjusting for study arm. The effect of each

covariate on symptoms of common mental disorders will be estimated as a relative risk (RR) from the Poisson regression model.

2) We will also conduct a per-protocol analysis using the same procedures described above, but only amongst participants who received full doses of the Youth Friendship Bench SA plus SOC intervention or SOC only.

Secondary Analysis 4: To qualitatively explore the acceptability, feasibility, and appropriateness of the Youth Friendship Bench SA intervention and the POC TFV urine assay.

- Qualitative factors that influence acceptability, feasibility, and appropriateness of the Youth Friendship Bench SA intervention

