Appendix – Table shells for primary and secondary analyses

Table 1: Co-Primary Analysis 1

Associations between Youth Friendship Bench SA intervention and PrEP adherence at Week 12, assessed via univariate and multivariable Poisson regression models with robust standard errors

Exposure group	Urine TFV ≥1500 ng/mL						
	ITT analysis (n = XX)			Per-protocol analysis (n = XX)			
	n (%)	RR (95% CI)	p -value	n (%)	aRR (95% CI)	p -value	
Intervention arm							

Standard-of-care

Table 2: Co-Primary Analysis 2

Associations between Youth Friendship Bench SA intervention and symptoms of common mental health disorders at Week 12, assessed via univariate and multivariable Poisson regression models with robust standard errors

Exposure group	SRQ-20 score < 7						
	ITT analysis (n = XX)			Per-protocol analysis (n = XX)			
	n (%)	RR (95% CI)	p-value	n (%)	aRR (95% CI)	p -value	
Intervention arm							

Standard-of-care

Table 3: Secondary Analysis 1

Associations between Youth Friendship Bench SA intervention and PrEP adherence at Week 4, assessed via univariate and multivariable Poisson regression models with robust standard errors

	Urine TFV ≥1500 ng/mL						
Exposure group	ITT analysis (n = XX)			Per-protocol analysis (n = XX)			
	n (%)	RR (95% CI)	p -value	n (%)	aRR (95% CI)	p -value	
Intervention arm							
Standard-of-care							

Table 4: Secondary Analysis 2

Correlates of PrEP adherence at Week 12 assessed via univariate and multivariable logistic regression models

Characteristic	Unadjusted model		Adjusted for study arm		
	OR (95% CI)	p -value	aOR (95% CI)	p -value	
Sexual behaviors					
Gender-based violence					
Symptoms of common mental disorders					
Self-esteem					
Level of engagement with intervention					

Table 5: Secondary Analysis 3

Correlates of symptoms of common mental health disorders at Week 12 assessed via univariate and multivariable logistic regression models

Characteristic	Unadjusted model		Adjusted for study arm		
	OR (95% CI) p -value		aOR (95% CI)	p -value	
Sexual behaviors					
Gender-based violence					
Symptoms of common mental disorders					
Self-esteem					
Level of engagement with intervention					

References

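### Secondary Analyses 2 and 3 select covariates and estimate their effects on the same women, with no post-selection or multiplicity control and no exploratory label

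*SAP*

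**What the plan says.** Both documents list the correlates analyses as secondary objectives. The one for adherence reads "To assess the correlates of PrEP adherence, after adjusting for study arm, including sociodemographic factors and psychosocial and behavioral characteristics", and a parallel objective covers symptoms of common mental disorders. The exploratory lists (Protocol 6.3; SAP, Study Objectives) hold only mediators and moderators.

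The SAP describes model building under Secondary Analysis 2:

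- Overall approach: "We will use a combination of consulting previous research, univariate analyses, and forward stepwise selection to determine which sociodemographic factors" and other characteristics enter the model.
- Univariate screen: "Based on this test, variables with a p-value greater than alpha-level of 0.05 will be included in our multivariable model".
- Forward selection by AIC and BIC, with the stop rule "We will repeat this process until no additions significantly improve the model fit". Which criterion governs is not stated.
- Estimation by Poisson regression with robust standard errors on the same participants: "The effect of each covariate on PrEP adherence will be estimated as a relative risk (RR) from the Poisson regression model".

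For Secondary Analysis 3, "We will use the same process described above using separate theoretical guidelines and univariable analyses for variable selection". Both analyses are repeated per protocol.

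The candidates for adherence are domains, not variables: sociodemographics, sexual behaviours, gender-based violence, "symptoms of common mental disorders; self-esteem; and level of engagement with the intervention". The number of variables is not given. The SAP speaks of hypothesis-generating results only where more than 40% of outcomes are missing.

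The table shells differ from the text. Table 4 is titled "Correlates of PrEP adherence at Week 12 assessed via univariate and multivariable logistic regression models". It and Table 5 have five fixed rows, with odds ratios, 95% CIs and p-values, unadjusted and adjusted for arm. Protocol 11.4.3 also specifies logistic regression and describes no selection.

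**The concern.** A covariate reaches the final model because its association with the outcome in these women was strong enough to pass the filter. Testing it again on the same women with an ordinary standard error treats it as if it had been chosen in advance. The nominal 5% error rate and 95% coverage then do not apply, and the estimates of selected covariates tend to lie too far from the null. There is also more than one candidate and more than one outcome, with nothing to control the number of chance findings.

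At stake is a chance association, for example of self-esteem or gender-based violence with adherence, reported as an effect under a secondary objective with nothing to warn the reader.

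**Working it through.** **Plan's own figure.** Neither document gives an error rate, power or sample size for these analyses, so there is nothing to reproduce.

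**Inputs from the documents.** 110 women randomized 1:1; 85-90% retained, so 110 × 0.85 = 93.5 to 110 × 0.90 = 99 evaluable; 40% adherence assumed under standard of care; 50% symptom prevalence assumed; selection steps as above.

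**Assumptions.** 6 or 12 binary candidates, each at 40% prevalence, latent correlation 0.2, all unrelated to the outcome; n = 96; arm kept in the model; outcome rates 0.3 to 0.6. Checks used n = 94, 99 and 110 and correlation 0.

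**Step 1: what entry by AIC means.** For a binary outcome with rate π, the Poisson likelihood-ratio statistic for one null covariate is approximately (1 − π) × X², where X² is the ordinary chi-squared on 1 df. Entry by AIC needs a statistic above 2, so X² > 2/(1 − π):

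- π = 0.3: 2/0.7 = 2.86, p = 0.091
- π = 0.4: 2/0.6 = 3.33, p = 0.068
- π = 0.5: 2/0.5 = 4.00, p = 0.046
- π = 0.6: 2/0.4 = 5.00, p = 0.025

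With BIC the penalty is ln(96) = 4.56. At π = 0.5, X² must exceed 9.13 (p = 0.0025). Entry is therefore close to a significance test, or stricter than one. It also follows that at π = 0.5 a screen keeping p>0.05 and Poisson AIC entry at p<0.046 hardly overlap, so few covariates can enter under the screen as written.

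**Step 2: simulated selection, all candidates null (700-1,500 trials per setting).**

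| Screen | Model and criterion | Null entrants with p<0.05 | Trials with at least one false correlate |
|---|---|---|---|
| p<0.05 | Poisson, AIC | 76-97% | 19-25% (6 candidates), 27-40% (12), both AIC models |
| p<0.05 | Logistic, AIC | 77-85% | as above |
| p<0.05 | Poisson or logistic, BIC | 100% | logistic: 19% (6), 32% (12) |
| p>0.05, as written | Poisson, AIC | 28-56% | 0.3-11% |
| p>0.05, as written | Logistic, AIC | 12-21% | 7% (6) |
| p>0.05, as written | Poisson, BIC | none entered | 0% |
| p>0.05, as written | Logistic, BIC | 100%, but rarely enters | about 0.3-1% |

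The 28-56% leaves out an outcome rate of 0.6, where the share was 71% but rested on about 7 entries in 1,500 trials.

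A separate simulation (n = 98, outcome rate 0.5, p<0.05 screen, AIC) agrees. With 10 candidates it gave 94% of entrants and 33% of trials under Poisson, and 73% and 36% under logistic. With 6 candidates and Poisson it gave 22% of trials.

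A further check (500 trials, n = 96, rate 0.5, correlation 0.2) covered the cell missing from the table. With the written screen, logistic AIC and 12 candidates, 22% of entrants were significant, and 22% of trials had at least one false correlate. The low Poisson range therefore does not carry over to the logistic model when there are many candidates.

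**Step 3: no selection, fixed rows as in Tables 4-5.** Each row has its nominal 5% error. For five independent tests, 1 − 0.95⁵ = 0.226, about 23% per outcome.

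**Step 4: after pre-listing every candidate.** Each null covariate is significant in about 5-7% of trials. The chance of at least one is 1 − 0.95⁶ = 26% for 6 independent candidates and 1 − 0.95¹² = 46% for 12. Pre-listing removes the selection bias but not the multiplicity.

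**The case against.** **The screen as written runs the other way.** It keeps p>0.05, so the high figures in the table are not the plan's literal rates. This stands. A reader might infer that null covariates entering the model nearly always look significant. The documents do not support that without a condition: it needs the screen to be read as p<0.05, and even then logistic AIC gives 73-85%. But a screen that discards the associated covariates is hard to take as intended, and correcting it alone brings the selection problem in.

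**The text promises only a relative risk.** P-values and CIs appear in Tables 4-5, which have fixed rows and do not clearly show a selected model. This stands in part. The text does specify robust standard errors for the selected model and says its AIC and BIC will be in the table. The shells are also titled multivariable. Which model fills them is unresolved.

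**Candidates are first narrowed by prior research, so all-null is a worst case.** This is fair. The Protocol background reports an association of persistent symptoms with adherence. The simulated rates describe null candidates only.

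**Pooling overstates multiplicity.** A reader might combine ten rows across Tables 4 and 5 into 1 − 0.95¹⁰ = 40%. That crosses two separate outcomes and counts a symptoms row in Table 5 that the SAP's covariate list for Secondary Analysis 3 omits. The 23% per outcome is the defensible figure, and it is secondary to the selection problem.

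**Conclusion.** The concern holds in a conditional form. Selection and inference use the same 94-99 women, and nothing in either document corrects, controls or labels the result.

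- With the screen at p<0.05, roughly 75-95% of null covariates entering under AIC look significant. At least one false correlate appears in about 18-25% of trials with 6 candidates and 27-40% with 10-12.
- With the screen as written, the share of entrants that look significant is much lower, and with the SAP's Poisson model so is the trial-level rate. That is the by-product of a separate defect, not protection.
- If only the fixed rows are reported, selection bias is absent and about a 23% chance of a false positive per outcome remains.

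These sizes rest on the assumed number, prevalence and correlation of candidates and on all of them being null. The effect is confined to secondary analyses, because the co-primary intent-to-treat models contain arm only.

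**What to change.** In the SAP, for Secondary Analyses 2 and 3:

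1. Pre-list the candidate variables for each outcome, including the sociodemographic ones that Tables 4-5 lack and a decision on the symptoms row in Table 5.
2. Report every candidate in Tables 4-5 with its arm-adjusted estimate and 95% CI, selected or not, and use one effect measure in text and shells.
3. If a stepwise model is kept, name the criterion and show the model as descriptive, without p-values or the word *effect*.
4. Label both analyses hypothesis-generating. If p-values are kept, take them from the unselected arm-adjusted models and apply Benjamini-Hochberg within each outcome.

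The direction of the univariate screen needs its own correction; it ceases to matter here if selection is dropped. The cost is SAP wording, slightly longer tables and fewer correlates called significant. No new data are needed.

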9.3. Adverse Event Definition and Reporting

For the purposes of this study, only serious adverse events (SAEs) and adverse events of special interest (AESIs) will be recorded. These will be summarized by arm, as a secondary outcome of our study. SAEs are defined as those events that result in death, are life-threatening, require inpatient hospitalization or prolongation of existing hospitalization, and/or result in persistent or significant disability/incapacity. AESIs are considered reports of self-harm or self-injury.

With appropriate permission of the participant, whenever possible, records from all non-study medical providers related to SAEs will be obtained and required data elements will be recorded

on study CRFs. All participants reporting an AE will be followed clinically, until the AE resolves (returns to baseline) or stabilizes.

Site staff will also report information regarding SAEs to their IRB or other local regulatory agencies in accordance with all applicable regulations and local IRB requirements.

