- To assess the correlates of symptoms of common mental disorders, after adjusting for study arm, including sociodemographic factors and psychosocial and behavioral characteristics.
- To qualitatively explore the acceptability, feasibility, and appropriateness of the Youth Friendship Bench SA intervention and the POC TFV urine assay.
- To monitor and describe the occurrence of serious adverse events over the study (defined as those events that result in death, are life-threatening, require inpatient hospitalization or prolongation of existing hospitalization, and/or result in persistent or significant disability/incapacity) plus adverse events of special interest (reports of self-harm or selfinjury).

The exploratory objectives of this study are:

- To explore mediators and moderators of the Youth Friendship Bench SA intervention effect on PrEP adherence.
- To explore mediators and moderators of the Youth Friendship Bench SA intervention effect on symptoms of common mental disorders.

Study Design

This is as single-site effectiveness-implementation randomized controlled trial. 110 participants are planned and will be consented to have 12 weeks of follow-up. All participants will be offered PrEP by clinic personnel as part of standard PrEP prescribing practices, and PrEP delivery (including PrEP readiness assessment, HIV testing, PrEP adherence counseling that is not part of the urine point-of-care drug-level feedback, and PrEP prescribing) is not considered a research procedure.

Each participant will be randomized in a 1:1 ratio to receive either standard-of-care plus our Youth Friendship Bench SA mental health intervention package or standard-of-care alone. Our co-primary endpoints are PrEP adherence assessed using tenofovir detected in a urine POC assay performed at the Week 12 study visit and symptoms of common mental disorders assessed using the SRQ-20 at the Week 12 visit. All participants will also receive PrEP adherence counseling based on results of their urine POC TFV assay at the Week 4 and 12 visits ("druglevel feedback counseling"), in addition to their standard-of-care or Youth Friendship Bench SA services.

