	The mental health related primary outcome is the proportion with reduced symptoms of common mental disorders (SRQ-20 scores <7) at Month 3, measured using the SRQ-20
Study Duration:	Approximately 36 months, including submissions to Institutional Review Boards (IRBs) and study start up activities (6 months), recruitment and enrollment (12 months), participant follow up (3 months following the last enrolled participant), and data analysis (remaining time through 36 months).
Study Site:	Ward 21 public clinic in Johannesburg, South Africa.

Overview of Study Design

Figure 1. Study schema for the evaluation of the Youth Friendship Bench SA counseling intervention

Sample size

We will randomize 110 AGYW in a 1:1 ratio to either our adapted intervention or standard-of-care mental health services over a 12-month study period (approximately 9-10 AGYW enrolled per month). Based on current levels of AGYW receiving PrEP at the public health clinic in Johannesburg, and reporting symptoms of common mental disorders and receiving referral services, we will likely need to screen approximately 18-20 AGYW per month to meet our enrollment targets. Based on prior PrEP studies with AGYW in this setting (HPTN 082, PrEP SMART, POWER), we expect to retain 85-90% of AGYW through three months of follow-up.

Power calculations

For our primary outcome of PrEP adherence, if we assume 40% PrEP adherence in the standardof-care arm (as was seen in the HPTN 082 trial with AGYW in this setting) and an alpha of 0.05, we will have 80% power to detect at least a 20% difference in the proportion with adherence between arms.

For our primary outcome of common mental disorder symptoms, if we assume 50% prevalence of symptoms of common mental disorders (again, as was seen in the HPTN 082 and PrEP SMART trials) and an alpha of 0.05, we will have 80% power to detect at least a 25% difference in the proportion with symptoms of common mental disorders between arms.

Data Analysis

Co-Primary Analysis 1: To compare the proportion of young South African women who adhere well to PrEP (based on tenofovir [TFV] levels from a urine point-of-care [POC] assay) between those receiving the Youth Friendship Bench SA plus standard-of-care (SOC) mental health services versus receipt of standard-of-care services alone, after 3 months

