- SAEs (including events that result in death, are life-threatening, require inpatient hospitalization or prolongation of existing hospitalization, and/or result in persistent or significant disability/incapacity) and adverse events of special interest (reports of self-harm or self-injury).
- We will analyze qualitative data (in-depth interviews, clinic observation field notes) using an inductive and deductive coding approach and will use descriptive statistics to summarize quantitative data on intervention acceptability, feasibility, and appropriateness and SAEs and AESIs.

Secondary Analysis 5: To monitor and describe the occurrence of serious adverse events over the study (defined as those events that result in death, are life-threatening, require inpatient hospitalization or prolongation of existing hospitalization, and/or result in persistent or significant disability/incapacity) plus adverse events of special interest (reports of self-harm or self-injury).

Statistical analyses:

1) We will compute descriptive statistics to describe the occurrence of serious adverse events and adverse events of special interest. For the full study population, we will compute means, standard deviations, medians, and inter-quartile ranges for each of the adverse events that may occur. Chi-squared tests will be used to assess differences in adverse study events across meaningful groupings, such as between study arms.

Exploratory Objective 1: To explore mediators and moderators of the Youth Friendship Bench SA intervention effect on PrEP adherence.

- Mediators and moderators of the Youth Friendship Bench SA intervention effect on PrEP adherence at 12 weeks
- Covariate characteristics assessed at baseline and follow-up may include Sociodemographic characteristics; sexual behaviors; gender-based violence (GBV); symptoms of common mental disorders; self-esteem; intervention acceptability, feasibility, and appropriateness; and level of engagement with the intervention.

Exploratory Objective 2: To explore mediators and moderators of the Youth Friendship Bench SA intervention effect on symptoms of common mental disorders.

• Mediators and moderators of the Youth Friendship Bench SA intervention effect on symptoms of common mental disorders at 12 weeks

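### The SAP's safety analysis gives full-population means and quartiles plus an unspecified chi-squared test, where by-arm participant counts with an exact interval are needed

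*SAP*

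**What the plan says.** SAP Secondary Analysis 5 covers SAEs and the adverse events of special interest (AESIs), which are reports of self-harm or self-injury. For the full study population, "we will compute means, standard deviations, medians, and inter-quartile ranges for each of the adverse events that may occur". It then adds: "Chi-squared tests will be used to assess differences in adverse study events across meaningful groupings, such as between study arms". It does not say whether a continuity correction applies, what happens when expected counts are small, or whether the unit is the participant or the event. It asks for no count and percent of participants with an event and no effect estimate. The SAP appendix has no table shell for safety.

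Protocol section 9.3 says that "only serious adverse events (SAEs) and adverse events of special interest (AESIs) will be recorded", and continues: "These will be summarized by arm, as a secondary outcome of our study". Protocol section 11.4.3 and SAP Secondary Analysis 4 mention only descriptive statistics for these events. Neither document states an expected rate of SAEs or self-harm.

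**The concern.** There are two separate weaknesses.

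The first is the summary. SAEs and self-harm reports are yes/no for most participants, and the chosen statistics suit a continuous measurement. They are also tied to the whole study population, so the only by-arm output that the SAP prescribes is a p-value. That falls short of the by-arm summary in protocol section 9.3.

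The second is the test. With 55 women per arm, 12 weeks of follow-up, and enrolment closed to women reporting suicidal intent or self-harm (protocol section 7.3.3), event totals may well be small. At some small totals, whether p falls below 0.05 depends on which form of chi-squared is run, and the SAP leaves that open. Self-harm is the event of special interest in a mental health trial, so a nominally significant p-value could be taken as harm or benefit when it reflects a software default. The open-ended choice of groupings adds to this.

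**Working it through.** **Inputs.** The SAP sample size section says "We will randomize 110 AGYW in a 1:1 ratio to either our adapted intervention or standard-of-care mental health services over a 12-month study period", so there are 110/2 = 55 per arm. Follow-up is 12 weeks (SAP Study Design). Expected retention is 85–90%, or about 47 to 50 per arm (0.85 × 55 = 46.75; 0.90 × 55 = 49.5). No alpha is stated for the safety tests, so 0.05 two-sided is assumed. No event rate is stated, so small totals are assumed and a range of rates is shown. The plan gives no safety figure to reproduce.

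**Summaries.** If fewer than a quarter of 110 women have an event (up to 27, since 110/4 = 27.5), the median and both quartiles are 0. For a yes/no event with proportion p, the mean is p and the SD is approximately √[p(1 − p)], so the SD is fixed by the mean. With 4 events in 110, the mean is 4/110 = 0.036 and the SD is √(0.036 × 0.964) = 0.187. Neither says how the four were split between arms.

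**One table by hand, 4 v 0 at 55 per arm.** The cells are 4, 51 and 0, 55. The column totals are 4 and 106, and the expected events are 4/2 = 2 per arm.
- Uncorrected: χ² = N(ad − bc)²/(product of margins) = 110 × (4×55 − 51×0)²/(55 × 55 × 4 × 106) = 110 × 220²/1,282,600 = 4.15, p = 0.042.
- Yates: replace 220 by 220 − 110/2 = 165. χ² = 110 × 165²/1,282,600 = 2.33, p = 0.127.
- Fisher: 2 × C(55,4)/C(110,4) = 2 × 341,055/5,773,185 = 0.118.

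**Other tables at 55 per arm.**

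| Events | Expected per arm | Uncorrected | Yates | Fisher |
|---|---|---|---|---|
| 4 v 0 | 2 | 0.042 | 0.127 | 0.118 |
| 5 v 0 | 2.5 | 0.022 | 0.067 | 0.057 |
| 6 v 0 | 3 | 0.012 | 0.036 | 0.027 |
| 7 v 1 | 4 | 0.028 | 0.066 | 0.060 |
| 8 v 2 | 5 | 0.047 | 0.097 | 0.093 |

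At 50 and at 47 per arm, 4 v 0 still gives 0.041 uncorrected, against 0.118 and 0.117 by Fisher's test.

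**Type I error given the total number of events** (hypergeometric, no true difference). With 4 events, uncorrected chi-squared rejects 11.8% of the time and Fisher's test 0%. With 10 events the figures are 9.3% and 1.6%. With 1 to 3 events neither can reject. With 6, 7, 9 or 12 events the two reject equally often (for example 2.7% each at 6).

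**Type I error over all totals** (two binomials of 55 with the same assumed rate).

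| Assumed rate | Uncorrected | Fisher |
|---|---|---|
| 1% | 0.3% | 0.0% |
| 2% | 1.6% | 0.05% |
| 3% | 3.2% | 0.2% |
| 5% | 4.5% | 0.9% |
| 10% | 5.0% | 2.0% |

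**Power at assumed true rates of 1% v 8%:** 43% for uncorrected chi-squared and 18% for Fisher's test.

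**The case against.** A reader might infer from 0.042 against 0.118 that the planned test gives p-values that are too small and will over-declare safety differences. The calculations do not support that. Over all possible totals, uncorrected chi-squared stays at or below 5% at assumed rates of 1–10%. Much of the gap is Fisher's conservatism, and the excess appears only at particular totals such as 4 or 10. The tables where the tests disagree are a selection. The 8 v 2 table even has expected counts of 5, so the usual rule of thumb would pass it. With Yates correction the disagreement in the four discordant tables (4 v 0, 5 v 0, 7 v 1, 8 v 2) goes away. A plain switch to Fisher's test also has a cost in a safety setting, because it is less likely to flag a real imbalance. All of this stands.

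It can also be said that a mean of a 0/1 variable is the proportion, that mean events per woman is a legitimate summary when events recur, that the protocol already promises a by-arm summary, that the objective is to monitor and describe, and that a DSMB reviews SAE data. These are fair, and they make the point small. They do not supply what the SAP omits: participant counts by arm, an effect estimate, a named test variant and a unit of analysis. The protocol's promise makes the omission an inconsistency between the documents.

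**Conclusion.** The point holds as a minor improvement to a secondary analysis. The prescribed summaries are uninformative if under a quarter of women have an event, and they leave out the by-arm description in protocol section 9.3. The prescribed test is under-specified, so at some small totals nominal significance depends on an unstated choice (4 v 0: 0.042, 0.127 or 0.118).

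The documents do not show inflated overall error, and they do not show that events will be few. That second premise is an assumption. It is plausible because only SAEs and self-harm or self-injury are recorded, over 12 weeks, with self-harm an exclusion at entry. The p-values assume 55 per arm and a two-sided 0.05 level; 4 v 0 changes little at 47 to 50 per arm. No decision rule rests on this test, and the co-primary results are unaffected.

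**What to change.** In SAP Secondary Analysis 5, replace the means, SDs, medians and quartiles with the following, by arm:
- number and percent of participants with at least one SAE;
- number and percent with at least one self-harm or self-injury event;
- total number of events of each kind;
- risk difference with an exact 95% CI.

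State that the comparison is descriptive and that the estimate and interval lead. If a p-value is shown, count participants rather than events, since repeat events in one woman are not independent. Name one small-count method in advance, for example an unconditional exact test or Fisher's exact test. If Fisher's test is chosen, acknowledge its conservatism (type I error 0–2% at assumed rates of 1–10%) and its lower power. List the groupings to be compared, and add a safety table shell to the appendix.

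The cost is SAP wording and one table shell. No new data, visits or participants are needed.
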